6.5. Treatment Compliance

All doses will be administered by qualified clinical study center personnel and any missed doses will be reported and recorded on the eCRF.

7. STUDY ASSESSMENTS

The schedules of assessments are provided in [Table 1](#) for Part A; and in [Table 2](#), [Table 3](#), and [Table 4](#) for Part B.

7.1. Screening/Baseline Assessments

Subject/patient demographic data and complete medical history (including documentation or confirmation of PH1) will be obtained at Screening. Screening safety assessments are included in the Schedule of Assessments, with additional details provided in [Section 7.5](#), as applicable.

7.1.1. Renal Function in Part B

7.1.1.1. Urinary Oxalate Excretion and Creatinine Clearance

During the screening period, 24-hour urine collections will be completed at 2 separate time points. The first screening 24-hour urine collection will be used to assess eligibility. The second screening 24-hour urine collection will only be initiated after eligibility is confirmed. Blood samples for serum creatinine will be obtained throughout the study as part of clinical laboratory assessments (see [Section 7.5.6](#)) for the calculation of creatinine clearance.

Patients will be instructed to collect urine samples for the full 24-hour period; however, after confirming eligibility, for patients unable to collect urine samples for the full 24-hour period, urinary oxalate excretion may be calculated from samples collected over an 18 to 24 hour period.

Patients will have the option to bring the 24-hour urine collections to the clinical study center at specified follow-up visits, courier samples to the clinical study center or to the vendor performing analyses, or elect to have the 24-hour urine collected during an inpatient stay at the clinical study center for other assessments.

7.1.1.2. Estimated Glomerular Filtration Rate

eGFR (mL/min/1.73m²) will be calculated to confirm eligibility and to assess renal function during the study. The calculation will be based on the Modification of Diet in Renal Disease (MDRD) formula for patients ≥ 18 years of age and the Schwartz Bedside Formula for patients < 18 years of age (Appendix 11.2).[10, 11]

7.2. Pharmacodynamic Assessments

Urine and blood samples will be collected for assessment of PD parameters (oxalate and glycolate concentrations) at the time points in the Schedule of Assessments.

In Part B, single, 24-hour urine collections [REDACTED] will be collected for the analysis of urinary glycolate and oxalate excretion, and creatinine clearance. The 24-hour urine collection starting on Day -1 must conclude on Day 1 before administration of the first dose of study drug. Blood samples will also be collected for the analysis of plasma glycolate concentration.

Options for providing 24-hour urine collections to the clinical study center are in Section 7.1.1.1.

Details regarding the processing and aliquoting of samples for storage and PD analyses will be provided in the Laboratory Manual.

7.3. Pharmacokinetic Assessments

Blood and urine samples will be collected for assessment of ALN-GO1 PK parameters in Part A and Part B of the study at the time points in the Schedule of Assessments. In Part B, samples may also be analyzed for the [REDACTED]. A detailed schedule of time points for the collection of blood and urine samples for PK analysis is in Table 10 for Part A and in Table 11 and Table 12 for Part B in Appendix 11.1.

Options for providing urine collections to the clinical study center are in Section 7.1.1.1.

The concentration of ALN-GO1 will be determined using a validated assay. Details regarding the processing, shipping, and analysis of the samples will be provided in the Laboratory Manual.

7.4. Exploratory Assessments

Blood and urine samples will be collected for exploratory analyses of plasma oxalate concentration [REDACTED]

[REDACTED]

[REDACTED]

[REDACTED]

[REDACTED]

[REDACTED]

Details regarding the collection, processing, storage, and shipping of samples will be in the Laboratory Manual.

7.5. Safety Assessments

The assessment of safety during the course of the study will consist of the surveillance and recording of AEs, including serious adverse events (SAEs), recording of concomitant medication and measurements of vital signs, weight, physical examination and ECG findings, and clinical laboratory assessments; Echo assessments will also be evaluated in Part B only.

Safety will be monitored over the course of the study by an SRC as described in Section 4.6.

7.5.1. Vital Signs

Vital sign measurements include blood pressure, heart rate, body temperature, and respiratory rate. Vital signs will be measured in the supine position (should be consistent for each patient), after the subject/patient has rested comfortably for 10 minutes. Body temperature will be measured using a tympanic or oral thermometer. A patient's body temperature should be measured using the same method throughout the course of the study.

7.5.2. Weight and Height

Body weight will be measured in kilograms. Body mass index will be calculated from the height and weight. For patients <18 years of age, height will be measured in centimeters, and in triplicate, to facilitate calculation of eGFR using the Schwartz Bedside Formula.

7.5.3. Physical Examination

A full physical examination will include general appearance, eyes, ears, nose and throat, chest/respiratory, heart/cardiovascular, gastrointestinal/liver, musculoskeletal/extremities, dermatological/skin, thyroid/neck, lymph nodes, and neurological/psychiatric assessments.

A symptom-directed physical examination will include the evaluation of changes in symptoms, or the onset of new symptoms, since the last visit.

7.5.4. Electrocardiogram

Triplicate 12-lead ECGs will be measured approximately 5 minutes apart. Recordings will be obtained after the subject/patient has rested comfortably in the supine position for approximately 10 minutes. Subjects/Patients should remain supine between ECGs. ECGs should be performed at approximately the same time of day throughout the study.

Additional ECGs may be collected at the discretion of the Investigator. The electrophysiological parameters assessed will include, but are not limited to, rhythm, ventricular rate, PR interval, QRS duration, QT interval, ST and T waves, Bazett-corrected QT interval (QTcB) and Fridericia corrected QT interval (QTcF).

The Investigator or designee is responsible for reviewing the ECGs to assess whether the results have changed since the Screening/Baseline visit and to determine the clinical significance of the results. For any clinically significant changes from the Screening/Baseline visit (eg, ischemic ECG changes, wave/interval changes, or arrhythmia), the Investigator must contact the Medical Monitor to discuss continued participation of the subject/patient in the study.

7.5.5. Echocardiography (Part B only)

Echo assessments will be performed according to instructions provided in a study manual. The Investigator or designee is responsible for reviewing the Echos to assess whether the results have changed since the Screening/Baseline visit and to determine the clinical significance of the results. For any clinically significant changes from the Screening/Baseline visit, the Investigator must contact the Medical Monitor.

7.5.6. Clinical Laboratory Assessments

Clinical laboratory tests will be evaluated as noted in the Schedule of Assessments. In the event of an unexplained clinically relevant abnormal laboratory test occurring after study drug administration, the test should be repeated and followed up at the discretion of the Investigator until it has returned to the normal range or stabilized, and/or a diagnosis is made to adequately explain the abnormality.

Hematology

Complete blood count with differential

Serum Chemistry

Sodium

Potassium

BUN

Phosphate

Creatinine and eGFR calculation (using the MDRD or Schwartz formula depending on age)

Albumin

Uric acid

Calcium

Total protein

Carbon dioxide/bicarbonate

Glucose

Chloride

Cardiac Enzyme

Troponin I

Liver Function Tests

AST

ALP

ALT

Bilirubin (total and direct)

Coagulation Panel

Prothrombin time

International Normalized Ratio

Activated partial thromboplastin time

Urinalysis

Visual inspection for appearance and color	Bilirubin
pH (dipstick)	Nitrite
Specific gravity	RBCs
Ketones	Urobilinogen
Albumin (optional)	Leukocytes
Glucose	Microscopy (if clinically indicated)
Protein	

Immunogenicity

Antidrug Antibodies

Pregnancy Testing (WOCBP only) β -human chorionic gonadotropin

Abbreviations: AST=aspartate transaminase; ALP=alkaline phosphatase; ALT=alanine transaminase; BUN=blood urea nitrogen; eGFR=estimated glomerular filtration rate; MDRD=modification of diet in renal disease; WOCBP=women of child bearing potential.

7.5.6.1. Immunogenicity

Blood samples will be collected to evaluate antidrug antibodies (ADA). Blood samples for ADA testing that are collected on the day of dosing must be collected before study drug administration. Blood samples to evaluate ADAs will be collected throughout the treatment and follow-up periods as detailed in the Schedule of Assessments. Confirmed positive ADA samples will be tested for cross-reactivity with DNA and nucleic acids.

Details regarding the processing, shipping, and analysis of the samples will be provided in the Laboratory Manual.

7.5.6.2. Pregnancy Testing

A pregnancy test will be performed for WOCBP only. A serum pregnancy test will be performed at Screening or after the onset of menarche if the patient was not of childbearing potential at screening, and urine pregnancy tests will be performed thereafter per the Schedule of Assessments and any time pregnancy is suspected. The results of the pregnancy test must be known before study drug administration. Women who are pregnant are not eligible for study participation. Any woman with a positive pregnancy test during the study will be discontinued from study drug, but will continue to be followed for safety. Women determined to be pregnant while on study will be followed until the pregnancy outcome is known (see Section 7.5.7.6 for follow-up instructions).

7.5.6.3. Drugs of Abuse

At Screening, urine will be tested for the following drugs of abuse: amphetamines, barbiturates, benzodiazepines, cannabinoids, opiates, cocaine, and methadone. If a subject/patient fails the screening, they will be excluded from the study, unless, in Part B only, the positive result is due to prescribed medications for patients. A repeat drug screen may only be performed when

methodological reasons are believed to have led to a false positive. Borderline positive results, unless covered by the preceding condition, are to be considered as positive and the subject/patient will be excluded from the study. If subjects/patients are found to be positive due to short term medication use, eg, antitussives medication, they may undergo a repeat drug screen to determine if they continue to meet study requirements.

All subjects/patients should refrain from consuming poppy seeds 48 hours before screening and then from 48 hours before study drug administration until follow-up has been completed. Poppy seed ingestion may cause a positive result for opiates in urine drug screen.

7.5.6.4. Maximum Blood Volume

The maximum blood volume for subjects in Part A will not exceed 500 mL over the course of the study.

In Part B, the maximum blood volume, which will be collected from pediatric patients over the course of the study, will be based on age and weight and will not exceed those specified in [Table 13](#) from the Feinstein Institute for Medical Research Human Subject Protection Program Guidance Document (Section 11.3 in the Appendix).[12] The maximum blood volume for adult and pediatric patients initially randomized to ALN-GO1 is not expected to exceed 400 mL over the course of the study. The maximum blood volume for adult and pediatric patients initially randomized to placebo is not expected to exceed 450 mL over the course of the study. The blood volume limits for patients in Part B are based on those for 6 year old girls in the 5th percentile for weight, the smallest patients who may be enrolled in the study.

7.5.7. Adverse Events

7.5.7.1. Definitions

Adverse Event

According to the International Conference on Harmonization (ICH) E2A guideline Definitions and Standards for Expedited Reporting, and 21 CFR 312.32, IND Safety Reporting, an AE is any untoward medical occurrence in a patient or clinical investigational subject administered a medicinal product and which does not necessarily have a causal relationship with this treatment.

Serious Adverse Event

A serious adverse event (SAE) is any untoward medical occurrence that at any dose:

- Results in death
- Is life-threatening (an event which places the patient at immediate risk of death from the event as it occurred. It does not include an event that had it occurred in a more severe form might have caused death)
- Requires in-patient hospitalization or prolongation of existing hospitalization
- Results in persistent or significant disability or incapacity
- Is a congenital anomaly or birth defect

- Is an important medical event that may not be immediately life-threatening or result in death or hospitalization but may jeopardize the patient and may require intervention to prevent 1 of the other outcomes listed in the definition above (eg, events include allergic bronchospasm requiring intensive treatment in an emergency room or at home, blood dyscrasias, convulsions, or the development of drug dependency or abuse).

Adverse Event Severity

AE severity should be graded using the Common Terminology Criteria for Adverse Events (CTCAE). Refer to CTCAE for unique clinical descriptions of severity (Grades I through IV) for each AE based on the following general guideline:

Grade I:	Mild; asymptomatic or mild symptoms; clinical or diagnostic observations only; intervention not indicated
Grade II:	Moderate; minimal, local or noninvasive intervention indicated; limiting age appropriate instrumental activity of daily living (eg, preparing meals, shopping for groceries or clothes, using the telephone, managing money)
Grade III:	Severe or medically significant but not immediately life-threatening; hospitalization or prolongation of hospitalization indicated; disabling; limiting self-care activity of daily living (ie, bathing, dressing and undressing, feeding self, using the toilet, taking medications, and not bedridden)
Grade IV:	Life-threatening consequences; urgent intervention indicated
Grade V:	Death related to an adverse event

Changes in severity should be documented in the medical record to allow assessment of the duration of the event at each level of severity. Adverse events characterized as intermittent require documentation of the start and stop of each incidence. When changes in the severity of an AE occur more frequently than once a day, the maximum severity for the experience that day should be noted. If the severity category changes over a number of days, then those changes should be recorded separately (with distinct onset dates).

AE severity and seriousness are assessed independently. ‘Severity’ characterizes the intensity of an AE. ‘Serious’ is a regulatory definition and serves as a guide to the Sponsor for defining regulatory reporting obligations (see definition for Serious Adverse Event).

Relationship of the Adverse Event to Study Treatment

The relationship of each AE to study treatment should be evaluated by the Investigator using the following criteria:

Definitely related:	A clinical event, including laboratory test abnormality, occurring in a plausible time relationship to the medication administration, and which cannot be explained by concurrent disease or other drugs or chemicals. The response to withdrawal of the drug should be clinically plausible.
---------------------	---

Possibly related:	A clinical event, including laboratory test abnormality, with a reasonable time sequence to the medication administration, but which could also be explained by concurrent disease or other drugs or chemicals. Information on the drug withdrawal may be lacking or unclear.
Unlikely related:	A clinical event, including laboratory test abnormality, with little or no temporal relationship to medication administration, and which other drugs, chemicals, or underlying disease provide plausible explanations.
Not related:	A clinical event, including laboratory test abnormality that has no temporal relationship to the medication or has more likely alternative etiology.

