7.5.7.2. Eliciting and Recording Adverse Events

Eliciting Adverse Events

The patient should be asked about medically relevant changes in his/her health since the last visit. The patient should also be asked if he/she has been hospitalized, had any accidents, used any new medications, or changed concomitant medication routines (both prescription and OTC). In addition to patient observations, AEs will be documented from any clinically relevant laboratory findings, physical examination findings, ECG changes, or other findings that are relevant to patient safety.

Recording Adverse Events

The Investigator is responsible for recording non-serious AEs that are observed or reported by the patient after administration of the first dose of study drug regardless of their relationship to study drug through the end of study. Non-serious AEs will be followed until the end of study.

The Investigator is responsible for recording SAEs that are observed or reported by the patient after the time when the informed consent is signed regardless of their relationship to study drug through the end of study. SAEs will be followed until satisfactory resolution, until baseline level is reached, or until the SAE is considered by the Investigator to be chronic or the patient is stable, as appropriate.

All AEs must be recorded in the source records for the clinical study center and in the eCRF for the patient, whether or not they are considered to be drug-related. Each AE must be described in detail: onset time and date, description of event, severity, relationship to investigational drug, action taken, and outcome (including time and date of resolution, if applicable).

For purposes of this study, ISRs are considered to be Adverse Events of Clinical Interest. These AEs will be recorded both on a supplemental eCRF and on an Adverse Event of Clinical Interest form. Refer to the eCRF completion guidelines for details on these forms.

For SAEs, record the event(s) in the eCRF. If the EDC system is unavailable, complete the back-up SAE form.

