7.4.1 Adverse Events

In Part A, summary tables for AEs will be presented by ascending ALN-GO1 dose level, in total with all subjects receiving ALN-GO1, and placebo with subjects/patients receiving placebo pooled across enrollment cohorts presented first. AEs will be summarized separately for the single-blind dosing period and the study.

In Part B, for patients who were randomized to placebo, an AE during the single-blind period is defined as an AE with onset date/time on and after the first dose date/time of placebo and prior to the first dose date/time of open-label ALN-GO1. For patients who were initially randomized to ALN-GO1 a AE during the single-blind period is defined as an AE with onset date/time on or after the first dose date/time of ALN-GO1 and up to, and including, Study Day 85. AEs for single-blind period will be summarized by regimen and ascending dose level of ALN-GO1 and pooled placebo across regimen and dose being presented first. Sub-total for each regimen and overall will also be presented.

In Part B, a summary of AEs for the single-blind period will be provided by regimen and ascending dose level of ALN-GO1 and pooled placebo presented first. Total for each regimen and overall of ALN-GO1 will also be provided.

In Part B, for all patients receiving ALN-GO1, either as single-blind or open-label administration, and in any sequence, a AE is defined as an AE with onset date/time on or after the first dose date/time of ALN-GO1 and up to the end of study. All AEs under ALN-GO1 will be summarized by regimen and ascending dose, sub-total for each regimen, and for overall. At each dose level and for the sub-total and overall, AEs with be summarized for patients with single-blind administration only and then for single-blind and open-label administration combined.

In each analysis above, an overview of adverse events will be provided which summarizes subject-level incidence (frequency) of all AEs, drug-related AEs, grade 3/4/5 AEs, drug-related grade 3/4/5 AEs, treatment-emergent SAEs, drug-related treatment-emergent SAEs, and AEs leading to discontinuation of study drug and/or deaths.

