The number and percentage of subjects with AEs will be summarized by system organ class and preferred term. Drug-related AEs, grade 3/4/5 AEs, drug-related grade 3/4/5 AEs, treatment-emergent SAEs, drug-related treatment-emergent SAEs, AEs leading to discontinuation of study drug, AEs leading to study drug dose interruption and drug-related AEs leading to discontinuation of study drug will be summarized by system organ class and preferred term. For these summaries, subjects with multiple adverse events will be counted only once per SOC and preferred term. Summaries of AEs leading to discontinuation of study drug and leading to study drug dose interruption will be presented as applicable for the single-blind period, ALN-GO1 dosing period, and ALN-GO1 quarterly dosing period. Other summaries will be presented separately for the time periods in Sections 7.2.1 and 7.2.2.

In addition, summaries will be provided by the worst NCI-CTCAE grade, system organ class and preferred term for the number and percentage of subjects with AEs and drug-related AEs.

Listings will be provided for AEs leading to deaths, SAEs, and AEs leading to discontinuation of study drug or dose interruption.

By-subject AE data listings which will include at a minimum, subject/patient identifier, study drug taken prior to or on an AE onset date/time, verbatim term, preferred term, system organ class, NCI-CTCAE grade, relationship to study drug, action taken with study drug, SAE classification (Yes/No) and AE onset and end date/time. In addition, for Part A, AE and study day will also be included. In Part B, classification (yes/no) as a AE during the single-blind dosing period and the ALN-GO1 dosing period will be included. In Part B, study day and day relative to ALN-GO1 dosing will be included.

By-subject AE listings will be provided for Part A and Part B separately.

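### In Part B, the SAP's onset-date rule counts a placebo-period adverse event that only improves in grade after crossover as an ALN-GO1 adverse event

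*Protocol*

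**What the plan says.** Protocol 7.5.7.1 (Adverse Event Severity) sets the recording rule for a severity category that shifts over several days: "those changes should be recorded separately (with distinct onset dates"). It does not distinguish worsening from improvement. Changes more frequent than once a day are treated differently: "the maximum severity for the experience that day should be noted". Protocol 7.5.7.2 adds: "Each AE must be described in detail: onset time and date, description of event, severity".

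SAP 7.4.1 then assigns AEs to periods in Part B by onset. For a patient randomized to placebo, a single-blind-period AE is "an AE with onset date/time on and after the first dose date/time of placebo and prior to the first dose date/time of open-label ALN-GO1". For everyone who receives ALN-GO1, blinded or open-label and in any sequence, an ALN-GO1 AE is "an AE with onset date/time on or after the first dose date/time of ALN-GO1 and up to the end of study". Neither definition requires the event to be new, or worse than before. On repeats, the same section says "subjects with multiple adverse events will be counted only once per SOC and preferred term". It presents the ALN-GO1 summaries first for single-blind administration only, then with open-label administration added.

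**The concern.** The incidence of AEs is the primary endpoint (Protocol 3.1; SAP 5). In Part B every placebo patient is due to cross over to ALN-GO1, and the combined ALN-GO1 summaries include these patients. If a severity change creates a record with its own onset date, and the SAP looks only at onset date, a placebo-period event that is resolving after crossover enters the ALN-GO1 tables through its improvement.

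The result runs the wrong way: an event that persists at the same grade stays out of those tables, while one that gets better goes in. With dose columns as small as 4 patients, one record visibly changes a reported percentage.

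**Working it through.** No power or precision figure in the plan bears on this, so there is none to reproduce. The check applies the stated rules to example records and then does the cohort arithmetic.

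**Step 1: the rules applied.** Take a monthly-cohort placebo patient: first placebo dose on Day 1, first ALN-GO1 dose on Day 85 (SAP 7.4.2). The event days and grades are illustrative. A record counts under placebo if 1 ≤ onset day < 85, and under ALN-GO1 if onset day ≥ 85.

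| Event | Records | Placebo | ALN-GO1 |
|---|---|---|---|
| Grade 2 from Day 80, unchanged | Day 80 | yes | no |
| Grade 2 from Day 80, Grade 1 from Day 90 | Day 80; Day 90 | yes | yes |
| Grade 1 from Day 80, Grade 2 from Day 90 | Day 80; Day 90 | yes | yes |

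The third row is correct and depends on splitting: as a single record with onset on Day 80, the worsening would be missed under ALN-GO1. The second row is the fault. In the worst-grade table for ALN-GO1, that event would also appear at its lower, improved grade.

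**Step 2: does another rule prevent it?**
- The once-per-preferred-term rule removes repeats within a summary. It does not link a placebo-period record to an ALN-GO1-period record.
- Protocol 8.2.7 plans tabulations of treatment-emergent AEs, and SAP 7.4.1 refers to treatment-emergent SAEs. Neither document defines the term.
- The protocol's worsening condition is in the AE footnotes to Tables 1, 2 and 4 and concerns events present before any study drug. Table 3, the crossover schedule, has no such footnote.
- SAP 4.3.1 gives placebo patients a new baseline value before their first ALN-GO1 dose, but nothing equivalent is stated for AEs.

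**Step 3: who is exposed.** Protocol 4.1.2 has 4 patients per cohort randomized 3:1, so 4 × 1/4 = 1 placebo patient per cohort. Expansion patients never receive placebo. If all 24 Part B patients enroll:
- 4 cohorts and 2 expansions (16 + 8 = 24): 4 exposed
- 5 cohorts and 1 expansion (20 + 4 = 24): 5 exposed
- 6 cohorts, the maximum in the synopsis (6 × 4 = 24): 6 exposed

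**Step 4: size of one record.** If no other patient in the column has that preferred term under ALN-GO1, incidence moves from 0/N to 1/N, a rise of 100/N points. The column sizes come from the monthly display in SAP 7.2.3 (4 or 8 per dose, 8 or 16 in total).
- N = 4: 25 points
- N = 8: 12.5 points
- N = 16: 6.25 points

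**Step 5: the proposed rule tested.** Count a continuing event under ALN-GO1 only if its grade after the first ALN-GO1 dose exceeds its last grade before it. Improving case: 1 > 2 is false, so not counted. Worsening case: 2 > 1 is true, so counted.

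**The case against.** The strongest reply is that the protocol never calls a severity change a new AE. It asks for separate recording so that the duration at each severity level can be assessed, which fits one event with several severity entries. On that reading the AE's onset remains the placebo-period date and nothing is miscounted. The eCRF completion guidelines or the programming specifications, which are not among the documents, might link the entries. This stands as a real uncertainty about what would happen in practice. It does not remove the gap: the protocol gives the changes distinct onset dates, the SAP counts by onset date, and neither says which onset governs. SAP 8.2 describes the programming document as covering the format of outputs; a counting rule for the primary endpoint belongs in the SAP.

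Other replies limit the point and are accepted. By-subject listings show grade, onset and end times, relationship and day relative to ALN-GO1, so such a record could be found by inspection. All analyses are descriptive. The error over-counts events on drug and hides no harm.

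A reader might go further and infer that the placebo comparison is biased, or that improving events are attributed causally to the drug. The documents do not support either. The single-blind summary for placebo patients stops before their first ALN-GO1 dose, and the single-blind-only columns contain no crossover patients. The affected tables are all-causality counts; drug-related AEs are tabulated separately from the investigator's assessment.

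**Conclusion.** The concern holds for the all-causality ALN-GO1 and combined AE summaries in Part B. Following both documents as written, a placebo-period event that improves over days after crossover is counted there, while an unchanged one is not. The gap is in SAP 7.4.1; the protocol's splitting rule does useful work and is not at fault.

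The conclusion assumes that a separately recorded severity change enters the AE data as a record with its own onset date, and that no unseen document links it to the earlier record. It applies only to crossover patients with an AE ongoing at the first ALN-GO1 dose that later improves over more than a day. The 25 points at N = 4 is the most that one record can add, and is not a forecast. The documents do not support a claim that the primary endpoint is materially biased, but the rule should be settled before the tables are produced.

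**What to change.** Keep the protocol's splitting rule. In SAP 7.4.1, state that severity-change records of the same event are linked, and that an event ongoing at the first ALN-GO1 dose counts as an ALN-GO1 AE only if its grade after that dose exceeds its last grade before it. This follows the logic of SAP 4.3.1, which already resets the baseline at crossover, and of the protocol's worsening condition for events present before study drug.

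The cost is one SAP rule, one linking variable in the AE dataset and a little more programming. Visits, dosing and data collection schedules do not change.
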